10.2.5 Persistent iUPD

Progression is considered not confirmed, and the overall response remains iUPD, if:

- none of the progression-confirming factors identified above occurs, and
- the target lesion sum of diameters (initial target lesions) remains above the initial disease progression threshold (by RECIST 1.1).

Additional scans for confirmation are to be scheduled 4 to 8 weeks from the scans on which iUPD is seen. This may correspond to the next visit in the original visit schedule. The assessment of the subsequent confirmation scan proceeds in an identical manner, with possible outcomes of iCPD, iUPD, and iSD/iPR/iCR.

10.2.6 Resolution of iUPD

Progression is considered not confirmed, and the overall response becomes iSD/iPR/iCR, if:

- none of the progression-confirming factors identified above occurs, and
- the target lesion sum of diameters (initial target lesions) is not above the initial disease progression threshold.

The response is classified as iSD or iPR (depending on the sum of diameters of the target lesions), or iCR if all lesions resolve.

In this case, the initial iUPD is considered to be pseudoprogression, and the level of suspicion for progression is “reset”. This means that the next visit that shows radiographic progression, whenever it occurs, is again classified as iUPD by iRECIST, and the confirmation process is repeated before a response of iCPD can be assigned.

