10.2.2 Assessment and decision at RECIST 1.1 progression

Patients who show radiological disease progression by RECIST 1.1 will continue treatment until repeat scans are obtained, as described in section 8.1.2.

Tumor flare may manifest as any factor causing radiographic progression per RECIST 1.1, including:

- Increase in the sum of diameters of target lesion(s) identified at baseline to $\geq 20\%$ and ≥ 5 mm from nadir

Note: The iRECIST publication uses the terminology “sum of measurements”, but “sum of diameters” will be used in this Protocol, consistent with the original RECIST 1.1 terminology.

- Unequivocal progression of non-target lesion(s) identified at baseline
- Development of new lesion(s)

iRECIST defines new response categories, including unconfirmed progressive disease (iUPD) and confirmed progressive disease (iCPD). For purposes of iRECIST assessment, the first visit showing progression according to RECIST 1.1 will be assigned a visit (overall) response of iUPD, regardless of which factors caused the progression.

At this visit, target and non-target lesions identified at baseline by RECIST 1.1 will be assessed as usual.

New lesions will be classified as measurable or non-measurable, using the same size thresholds and rules as for baseline lesion assessment in RECIST 1.1. From measurable new lesions, up to 5 lesions total (up to 2 per organ) may be selected as new lesions – target. The sum of

diameters of these lesions will be calculated and kept distinct from the sum of diameters for target lesions at baseline. All other new lesions will be followed qualitatively as new lesions – non-target.

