10.2.4 Confirmation of progression

Progression is considered confirmed, and the overall response will be iCPD, if any of the following occurs:

- Any of the factors that were the basis for the initial iUPD to show worsening
 - For target lesions, worsening is a further increase in the sum of diameters of ≥ 5 mm, compared to any prior iUPD time point
 - For non-target lesions, worsening is any significant growth in lesions overall, compared to a prior iUPD time point; this does not have to meet the “unequivocal” standard of RECIST 1.1
 - For new lesions, worsening is any of these:
 - An increase in the new lesion sum of diameters by ≥ 5 mm from a prior iUPD time point
 - Visible growth of new non-target lesions
 - The appearance of additional new lesions
- Any new factor appears that would have triggered disease progression by RECIST 1.1

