10.2.8 Detection of progression at visits after pseudoprogression resolves

After resolution of pseudoprogression (i.e., after iSD/iPR/iCR), another instance of progression (another iUPD) is indicated by any of the following events:

- Target lesions
 - Sum of diameters reaches the disease progression threshold ($\geq 20\%$ and ≥ 5 mm increase from nadir) either for the first time or after resolution of previous pseudoprogression. The nadir is always the smallest sum of diameters seen during the entire trial, either before or after an instance of pseudoprogression.
- Non-target lesions
 - If non-target lesions have never shown unequivocal progression, their doing so for the first time results in iUPD.
 - If non-target lesions have shown previous unequivocal progression, and this progression has not resolved, iUPD results from any significant further growth of non-target lesions, taken as a whole.
- New lesions
 - New lesions appear for the first time
 - Additional new lesions appear
 - Previously identified new target lesions show an increase of ≥ 5 mm in the new lesion sum of diameters, from the nadir value of that sum
 - Previously identified non-target lesions show any significant growth

If any of the events above occur, the overall response for that visit is iUPD, and the iUPD evaluation process (see section [10.2.3](#)) is repeated. Progression must be confirmed before iCPD can occur.

The decision process on the subsequent iUPD is identical to the iUPD confirmation process for the initial disease progression, with one exception, which can occur if new lesions had occurred at a prior instance of iUPD, had not resolved, then worsened (increase in size or number)

leading to the second iUPD. If new lesion worsening has not resolved at the confirmatory scan, then iUPD cannot resolve to iSD or iPR. It will remain iUPD until either a decrease in the new lesion burden allows resolution to iSD or iPR, or until new or worsening causes of progression indicates iCPD.

Additional details about iRECIST are provided in the iRECIST publication.²⁰

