5.5.3.5. PFS and iPFS

PFS and iPFS are defined as the time from the first day of study treatment until the first date of radiological disease progression or death and will be summarized using Kaplan-Meier estimates in the efficacy population.

Patients with missing data will be censored/considered as having an event as specified in the table below.

Table 5 PFS and iPFS events and censoring

Situation	Date of progression or censoring	Outcome
Incomplete or no baseline tumor assessment.	First day of study treatment	Censored

Start of next-line anti-cancer therapy.	Date of the last tumor assessment with non-progression before the start of next-line anti-cancer therapy.	Censored
Death before the first disease progression assessment.	Date of death.	Progressed
Death between adequate tumor assessment visits.	Date of death.	Progressed
Progression or death after one missed adequate tumor assessment.	Date of progression or death, whichever is earliest (if both occur).	Progressed
Progression or death after more than one missed adequate tumor assessment.	Date of the last evaluable tumor assessment.	Censored
No progression, no death.	Date of the last evaluable tumor assessment.	Censored

For iPFS, the progression date to be used for calculation should be the first date at which progression criteria are met (i.e, the date of iUPD) provided that iCPD is confirmed at the next assessment. If iUPD occurs, but is disregarded because of later iSD, iPR, or iCR, that iUPD date should not be used as the progression event date.

If progression is not confirmed and there is no subsequent iSD, iPR, or iCR, the iUPD date should still be used if:

- the patient stops protocol treatment because they were not judged to be clinically stable, or
- no further tumor assessments are done, or
- the next timepoint responses are all iUPD, and iCPD never occurs, or
- the patient dies from his cancer.

PFS according to RECIST and iRECIST will be listed for ASaT population.

PFS according to RECIST and iRECIST will be displayed graphically using Kaplan-meier plots for efficacy and ASaT populations including count for numbers of patients at risk.

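### A first iUPD caused by a new or non-target lesion that merely stays unchanged is classed as resolved when the target sum is not above threshold, and the SAP then drops that progression date from iPFS, iTtP and iDoR

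*Protocol*

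**What the plan says.** Protocol 10.2.2 lists three routes to radiographic progression: growth of the target-lesion sum, unequivocal non-target progression, and new lesions. The first visit showing any of them "will be assigned a visit (overall) response of iUPD, regardless of which factors caused the progression".

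At the confirmatory scan, Protocol 10.2.4 gives iCPD on worsening ("Any of the factors that were the basis for the initial iUPD to show worsening") or on a further progression factor. If neither occurs, two sections divide the remaining patients:

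- 10.2.5 keeps the patient at iUPD when "the target lesion sum of diameters (initial target lesions) remains above the initial disease progression threshold (by RECIST 1.1").
- 10.2.6 declares the iUPD resolved when "the target lesion sum of diameters (initial target lesions) is not above the initial disease progression threshold", and then: "The response is classified as iSD or iPR (depending on the sum of diameters of the target lesions), or iCR if all lesions resolve". The iUPD is labelled pseudoprogression and the confirmation process starts afresh at the next progression.

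Protocol 10.2.8 adds a single exception for some later iUPDs: "If new lesion worsening has not resolved at the confirmatory scan, then iUPD cannot resolve to iSD or iPR".

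SAP 5.5.3.3 (iDoR), 5.5.3.5 (iPFS) and 5.5.3.7 (iTtP) share one dating rule. If an iUPD is followed by iSD, iPR or iCR, "that iUPD date should not be used as the progression event date". If every later timepoint is iUPD and iCPD never follows, the iUPD date counts as the event.

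**The concern.** Any of three factors can start an iUPD, but among patients who have not worsened only the target sum decides whether it has ended. If a new or non-target lesion was the cause and the target sum is not above its threshold, persistent iUPD cannot be reached. The patient is either iCPD or resolved, even with the causal lesion still present at the same size.

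The SAP then treats two equally unchanged progressions in opposite ways, keeping the target-driven one as an event and erasing the other. For an affected patient the error lengthens iPFS and iTtP, and lengthens iDoR in a responder. The planned sensitivity analysis in SAP 5.5.4 repeats the secondary analyses in the ASaT population, so it would not reveal the effect.

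**Working it through.** The plan gives no figure for this rule, so there is nothing to reproduce. The check is to enumerate the rules and follow example patients through the SAP.

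**Step 1. Classification after a first iUPD caused by a new or non-target lesion (Protocol 10.2.4 to 10.2.6).**

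| Causal lesion at rescan | Target sum above threshold | Target sum not above threshold |
|---|---|---|
| Worsened | iCPD | iCPD |
| Unchanged | iUPD | iSD, or iPR if the target sum meets partial response |
| Gone | iUPD | iSD or iPR as above (iCR only if all lesions resolve) |

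Apart from iCR, the last two rows are identical. Once the causal lesion has not worsened, its status has no effect on whether the patient is iUPD, iSD or iPR.

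**Step 2. Does 10.2.8 close the gap?** Its exception needs new lesions from a prior iUPD that had not resolved and then worsened, causing a second iUPD. It covers neither a first iUPD nor non-target lesions. The same section provides for non-target progression that is still unresolved after pseudoprogression has been declared over, which confirms that 10.2.6 is meant literally.

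**Step 3. iPFS and iTtP.** Scans at weeks 6, 12 and 18 on the 6-weekly schedule; iUPD at week 6; same picture at weeks 12 and 18; week 18 is the last scan.

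- New-lesion or non-target trigger, target sum not above threshold: iUPD, then iSD or iPR twice. The week-6 date is dropped and the patient is **censored at week 18**.
- Target trigger, sum still above threshold without further worsening: iUPD three times. **Event at week 6**.
- First patient, if iUPD were kept while the causal lesion persists: **event at week 6**.

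**Step 4. iDoR.** iPR at weeks 6 and 12, new-lesion iUPD at week 18, new lesion unchanged and targets still at partial response at weeks 24 and 30.

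- As written: censored at week 30, so 30 − 6 = **24 weeks, censored**.
- With iUPD kept: event at week 18, so 18 − 6 = **12 weeks, event**.

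**Step 5. iBOR, iCBR and iORR.** Under SAP 5.5.3.1, two iPR or iCR determinations more than 4 weeks apart give an iBOR of iPR (Step 2). One iSD or better at 42 days or later gives iSD (Step 3). Neither step excludes an earlier iUPD. However, the same section ends the best-response window at the first documented progression without saying whether iUPD or iCPD ends it. The effect on these endpoints is therefore conditional.

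**Step 6. Scale for iORR, using the planned 52 patients.** One patient is 1/52 = 1.9 points; three are 3/52 = 5.8 points. Taking the plan's desired rate as an illustrative level, 0.368 × 52 = 19.1, so 19 responders:

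- 19/52 = 36.5% (95% Clopper-Pearson CI 23.6 to 51.0)
- two fewer, 17/52 = 32.7% (20.3 to 47.1)

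**Step 7. RECIST 1.1.** SAP 5.5 (Table 2) maps the first iUPD to PD and derives no RECIST 1.1 response afterwards. The primary ORR, the futility rule in SAP 5.6.12 and the RECIST 1.1 secondary endpoints never reach 10.2.6.

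**The case against.** The strongest reply is that this is a deliberate convention. Protocol 10.2.8 presents its restriction as an exception, so the first iUPD is knowingly treated differently, and the protocol refers to the iRECIST publication for detail. If 10.2.6 follows that publication, changing it would produce endpoints that are no longer per iRECIST. The affected endpoints are secondary, no hypothesis is tested, and each has a RECIST 1.1 counterpart in which a divergence would show.

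Part of this stands. It limits the importance of the point and is a reason to report the as-written classification as well. It does not explain why unchanged target progression is an event while unchanged new-lesion progression is erased. Whether 10.2.6 matches the publication cannot be settled from the documents.

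A reader might infer more than the text supports in three ways:

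- **That the appendix looks at nothing but the target sum.** It does not. Growth of new or non-target lesions, or additional new lesions, gives iCPD under 10.2.4. The gap concerns only lesions that have not worsened.
- **That 10.2.8 contradicts 10.2.6.** Its exception is narrow, and other later iUPDs follow the initial rule.
- **That iORR is certainly inflated.** This depends on the open iBOR window and needs two qualifying iPR determinations. iBOR and iCBR also do not change for a patient with a qualifying iSD, or a confirmed iPR, before the iUPD.

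**Conclusion.** The point holds for iPFS and iTtP, and for iDoR among iRECIST responders: the rule favours longer times whenever a first iUPD comes from a new or non-target lesion that is unchanged at rescan while the target sum is not above threshold. For iBOR, iCBR and iORR the bias is possible, subject to how the iBOR window is read.

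The number of such patients cannot be derived. The documents give no rate of progression by new or non-target lesions alone, and no rate at which such lesions stay unchanged. Patients with no further scan, or who stop treatment because they are not clinically stable, with no later iSD, iPR or iCR, keep their iUPD date and are not affected. As an assumed range only, 0 to 3 patients reclassified to iPR would move iORR by 0 to 5.8 points. The primary conclusion of the trial is not at risk. The point is worth correcting before database lock because the iRECIST results are pre-specified secondary evidence and the error runs in one direction.

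**What to change.** In SAP 5.5.3, for analysis only, derive the iRECIST timepoint response from the target, non-target and new-lesion data. Treat an iUPD as resolved only if the factor that triggered it is no longer at progression level:

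- target trigger: sum not above the threshold;
- new-lesion trigger: lesions gone, or their sum or number decreased by an amount stated in advance;
- non-target trigger: progression no longer recorded.

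Otherwise keep iUPD, so that the SAP's existing rule for unbroken iUPD dates the event at the first iUPD. Report the classification as written in 10.2.6 alongside, as a sensitivity analysis.

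Two further statements are needed. SAP 5.5.3.1 should say whether iUPD or iCPD ends the iBOR window. SAP 5.5.3.3, 5.5.3.5 and 5.5.3.7 should say which date applies to the sequence iUPD, iUPD, iCPD. The current condition that iCPD be confirmed at the next assessment does not clearly assign the first date, and the derivation will make this sequence more common.

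Protocol 8.1.5 uses iRECIST for treatment decisions, so the site-level wording is a separate matter. The sponsor should reconcile 10.2.5, 10.2.6 and 10.2.8; this review does not say which clinical rule should apply.

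The cost is some programming and slightly less favourable iRECIST results. New-lesion diameters are already summarised under SAP 5.5.6.5. That non-target status is recorded at each scan in usable form is an assumption to check against the eCRF.

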10.2.7 Management following the confirmatory scan

If repeat scans do not confirm disease progression per iRECIST, as assessed by the investigator, and the patient continues to be clinically stable, study interventions are to continue and the regular scan schedule is to be followed. If disease progression is confirmed, patients may be discontinued from study interventions.

Note: If a patient has iCPD and clinically meaningful, study interventions may be continued after consultation with the sponsor. In this case, if study interventions are continued, tumor imaging should continue to be performed following the intervals as outlined in section [8.1](#).

10.2.8 Detection of progression at visits after pseudoprogression resolves

After resolution of pseudoprogression (i.e., after iSD/iPR/iCR), another instance of progression (another iUPD) is indicated by any of the following events:

- Target lesions
 - Sum of diameters reaches the disease progression threshold ($\geq 20\%$ and ≥ 5 mm increase from nadir) either for the first time or after resolution of previous pseudoprogression. The nadir is always the smallest sum of diameters seen during the entire trial, either before or after an instance of pseudoprogression.
- Non-target lesions
 - If non-target lesions have never shown unequivocal progression, their doing so for the first time results in iUPD.
 - If non-target lesions have shown previous unequivocal progression, and this progression has not resolved, iUPD results from any significant further growth of non-target lesions, taken as a whole.
- New lesions
 - New lesions appear for the first time
 - Additional new lesions appear
 - Previously identified new target lesions show an increase of ≥ 5 mm in the new lesion sum of diameters, from the nadir value of that sum
 - Previously identified non-target lesions show any significant growth

If any of the events above occur, the overall response for that visit is iUPD, and the iUPD evaluation process (see section [10.2.3](#)) is repeated. Progression must be confirmed before iCPD can occur.

The decision process on the subsequent iUPD is identical to the iUPD confirmation process for the initial disease progression, with one exception, which can occur if new lesions had occurred at a prior instance of iUPD, had not resolved, then worsened (increase in size or number)

leading to the second iUPD. If new lesion worsening has not resolved at the confirmatory scan, then iUPD cannot resolve to iSD or iPR. It will remain iUPD until either a decrease in the new lesion burden allows resolution to iSD or iPR, or until new or worsening causes of progression indicates iCPD.

Additional details about iRECIST are provided in the iRECIST publication.²⁰

10.3 Appendix 3: Hy's law

Drugs are likely to cause a high rate (10-50%) of fatal liver injury or need for transplant in patients with acute hepatocellular injury sufficient to cause jaundice. Hy's law is a rule of thumb that a patient is at high risk of a fatal drug-induced liver injury if given a medication that causes hepatocellular injury (not cholestatic injury) with jaundice.

Hy's law cases have three components:

- The drug causes hepatocellular injury, generally defined as an elevated ALT or AST by 3-fold or greater above the ULN. Often with aminotransferases much greater (5-10 \times ULN).
- Among patients showing such aminotransferase elevations, they also have elevation of their serum total bilirubin of greater than 2 \times ULN, without findings of cholestasis (defined as serum alkaline phosphatase (ALP) activity less than 2 \times ULN).

No other reason can be found to explain the combination of increased aminotransferase and serum total bilirubin, such as viral hepatitis, alcohol abuse, ischemia, preexisting liver disease, or another drug capable of causing the observed injury.²⁹

10.4 Appendix 4: Cockcroft-Gault formula

For males, creatinine clearance is estimated using the Cockcroft-Gault formula as follows:

$$\text{Creatinine clearance} = [(140 - \text{age}) \times \text{weight}] / (72 \times \text{serum creatinine})$$

Where age is in years, weight is in kilograms, and serum creatinine is in mg/dL. Actual, not ideal weight is to be used.

For females, creatinine clearance is estimated by multiplying the result of the above formula by 0.85.

10.5 Appendix 3: Abbreviations

Abbreviation	Term
ADA	Anti-drug antibody
ADCC	Antibody-dependent cellular cytotoxicity
AE	Adverse event
ALP	Alkaline phosphatase
ALT	Alanine aminotransferase
ASaT	All-subjects-as-treated
AST	Aspartate aminotransferase
AUC	Area under the concentration-time curve
BOR	Best overall response (according to RECIST 1.1)
BRAF	V-raf murine sarcoma viral oncogene homolog B1
CA	Competent authority
CBR	Clinical benefit rate (according to RECIST 1.1)
CD	Cluster of differentiation
CFR	Code of federal regulations
CI	Confidence interval
CL	Apparent systemic clearance
C _{max}	Observed maximum serum concentration
CR	Complete response (according to RECIST 1.1)
CRA	Clinical research associate
CRO	Contract research organization
CT	Computed tomography
CTCAE	Common Terminology Criteria for Adverse Events
ctDNA	Circulating tumor DNA
C _{trough}	Pre-dose concentration
DLT	Dose-limiting toxicity
DoR	Duration of response (according to RECIST 1.1)
EC	Ethics committee
ECG	Electrocardiography
ECOG	Eastern Cooperative Oncology Group
eCRF	Electronic Case Report Form
EEA	European Economic Area
EGFR	Epidermal growth factor receptor
Fc	Fragment crystallizable
FDA	US Food and Drug Administration
GCP	Good Clinical Practice

Abbreviation	Term
HBV	Hepatitis B
HCV	Hepatitis C
IB	Investigator's Brochure
iBOR	Best overall response (according to iRECIST)
iCBR	Clinical benefit rate (according to iRECIST)
ICF	Informed Consent Form
ICH	International Council for Harmonisation
iCPD	Confirmed progressive disease (according to iRECIST)
iCR	Complete response (according to iRECIST)
IDMC	Independent Data Monitoring Committee
iDoR	Duration of response (according to iRECIST)
IEC	Independent ethics committee
Ig	Immunoglobulin
IL	Interleukin
ILD	Interstitial lung disease
iORR	Objective response rate (according to iRECIST)
iPFS	Progression-free survival (according to iRECIST)
iPR	Partial response (according to iRECIST)
IRB	Institutional review board
iRECIST	Response Evaluation Criteria In Solid Tumors for immune-based therapeutics
ISC	Internal safety committee
iSD	Stable disease (according to iRECIST)
iTtP	Time to progression (according to iRECIST)
iTtR	Time to response (according to iRECIST)
iUPD	Unconfirmed progressive disease (according to iRECIST)
K-RAS	Kirsten rat sarcoma viral oncogene homolog
MRI	Magnetic resonance imaging
NK	Natural killer
NKG2A	Inhibitory natural killer cell receptor
NKG2D	Activating natural killer cell receptor
NKp30	Natural killer protein 30; activating natural killer cell receptor
N-RAS	Neuroblastoma rat sarcoma viral oncogene homolog
ORR	Objective response rate (according to RECIST 1.1)
OS	Overall survival
PFS	Progression-free survival (according to RECIST 1.1)

Abbreviation	Term
PFS2	Progression-free survival on next-line anti-cancer treatment
PK	Pharmacokinetic(s)
PP	Per Protocol
PR	Partial response (according to RECIST 1.1)
Q1	25 th percentile
Q3	75 th percentile
R _{AUC}	Accumulation ratio
RAS	Rat sarcoma viral oncogene homolog
R _{Cmax}	Accumulation ratio
RECIST 1.1	Response Evaluation Criteria In Solid Tumors version 1.1
RP2D	Recommended phase 2 dose
SAE	Serious adverse event
SAP	Statistical analysis plan
SD	Stable disease (according to RECIST 1.1)
SmPC	Summary of Product Characteristics
T _{1/2}	Apparent terminal elimination half-life
TEAE	Treatment-emergent adverse event
T _{max}	Time to maximum serum concentration
TtP	Time to progression (according to RECIST 1.1)
TtR	Time to response (according to RECIST 1.1)
ULN	Upper limit of normal
V _{ss}	Apparent volume of distribution at steady state
V _z	Apparent volume of distribution during terminal phase
WOCBP	Woman of childbearing potential

Abbreviations of commonly used weight, height, and volume measures are not listed above.

